### CD4+ T Lymphocyte Count

Obtain absolute CD4+/CD8+ counts and percentages. All laboratories must possess a CLIA certification or equivalent.

### Safety Labs

CBC with differential, chemistry panel including liver enzymes (ALT, AST, Alk Phos), total bilirubin, and serum creatinine. All safety labs will be performed at local certified laboratories.

### Fasting Stored Serum and Plasma

If participants come to the appointment and are not fasting, they will need to come back in fasting state for these evaluations within a 7-day window.

Serum (three 1 mL aliquots) and plasma (three 1 mL aliquots) will be collected as indicated in the schedule of events (entry, week 24, week48). Additionally, please collect 3mL of both serum and plasma in the event of study discontinuation and/or virologic failure. Frozen specimens will be collected, labeled with patients' PID, study week # and date of draw, and stored in a -70 degrees Celsius until batched processing can occur. The stored samples will be used for future measurements of metabolic and inflammatory markers which may include but are not limited to adiponectin, IL-6, IL-1B, PAI-1, and d dimer.

## **7.0 Toxicity Management**

Criteria for participant management, dose interruptions, modifications, and discontinuation of drug treatment will be mandated only for toxicities attributable to study drug (for Arm A participants). Toxicities due to drugs in the background regimen/entry regimen (for Arm B participants) should be managed according to standard clinical practice, with the goal of maintaining continuous therapy, if possible.

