## **5.0 Study Treatment**

### **5.1 Regimens, Administration, and Duration**

Study treatment is open label bictegravir + tenofovir alafenamide + emtricitabine (only bictegravir is investigational).

At entry participants will be randomized 1:1 by the study team to:

ARM A (immediate switch): Switch current ART to bictegravir + tenofovir alafenamide + emtricitabine for 48 weeks

or

ARM B (no switch): Continue current therapy for 48 weeks

If randomized to ARM A at study entry, the subject will substitute bictegravir + tenofovir alafenamide + emtricitabine for their entry ART regimen.

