### **7.2 Grade 3 Toxicity**

Participants who develop a Grade 3 AE or toxicity should have all antiretroviral medications, including study drug, withheld unless the investigator has compelling evidence that the AE has NOT been caused by the study drug. The study chair ([name]) should be notified of any Grade 3 or greater toxicity. The subject should be re-evaluated closely until the AE returns to Grade  $\leq 2$ , at which time study drug may be reintroduced at the discretion of [name] or according to standard practice.

If the same Grade 3 AE recurs within 4 weeks following reintroduction and it is thought to be related possibly, probably, or definitely to study drug, then study drug must be permanently discontinued. If the same Grade 3 AE recurs after 4 weeks but is not believed to be related to study drug, the management scheme outlined above may be repeated.

Participants experiencing Grade 3 or greater AEs (requiring permanent discontinuation of study drug) should be followed closely for resolution of the AE to Grade  $\leq 2$ , and [name] must be consulted.

Participants with Grade 3 asymptomatic laboratory abnormalities in cholesterol, triglycerides or bilirubin (if on atazanavir) may continue study drug.

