## 9.3 Primary Endpoint Assessments

The safety (frequency of maintaining HIV-1 RNA <50 copies/mL) and tolerability (frequency of study drug discontinuation due to study-drug related AEs and frequency of study-drug related ≥ Grade 3 lab or clinical events whether or not study drug was discontinued) of bictegravir + tenofovir alafenamide + emtricitabine in HIV-infected TW on female hormone therapy vs continued ART.

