## **10.4 Serious Adverse Event Reporting**

The serious adverse event (SAE) reporting requirements and definitions for this study will be in keeping with local McGovern School of Medicine policies and in keeping with the sponsor's requirement. The study agent for SAE reporting is bictegravir + tenofovir alafenamide + emtricitabine. SAEs must be documented on the Serious Adverse Event Reporting form (SAE Reporting Form) available in the Manual of Procedure. [name] must be notified for any Grade 3 or greater toxicity that does not have a clearly documented etiology of not related to study drug. All Grade 4 events, death, persistent or significant disability/incapacity, hospitalization or prolongation of hospitalization, or event that the site investigator deems medically significant and thought to be related possibly, probably, or definitely related to study drug must be reported by completing and faxing the SAE Reporting form to [contact].

SAEs must be reported during the protocol-defined SAE Reporting period, which is from enrollment until four weeks following the subject's last dose of study drug. After the end of the protocol-defined SAE Reporting Period stated above, the site must report serious, unexpected, clinically-suspected adverse drug reactions if the site staff becomes aware of the event on a passive basis, i.e., from publicly available information.

All confirmed virologic failures will be reported immediately to the SMC. The SMC will also receive quarterly SAE reports for review.

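### Two of the three primary components count study-drug events against an arm that takes no study drug, and the primary as-treated set may drop the discontinuations being counted

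*Combined protocol and SAP*

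**What the plan says.** Section 9.3 has three primary components. Safety is the frequency of keeping HIV-1 RNA below 50 copies/mL. Tolerability is the "frequency of study drug discontinuation due to study-drug related AEs and frequency of study-drug related" Grade 3 or higher laboratory or clinical events, the latter counted "whether or not study drug was discontinued". All are stated "in HIV-infected TW on female hormone therapy vs continued ART".

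Section 9.6.1 compares the primary endpoint between arms by the Wilcoxon rank-sum test. The primary set is as-treated and leaves out participants who come off their regimen or lack an observed endpoint. A further sentence says that anyone off study drug or entry regimen for 14 consecutive days gives no data after the stop date. Intent-to-treat is a supplement.

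Section 5.1: "Study treatment is open label bictegravir + tenofovir alafenamide + emtricitabine"; Arm B continues its current therapy. Section 10.4: "The study agent for SAE reporting is bictegravir + tenofovir alafenamide + emtricitabine".

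Under section 7.0, criteria for interruption and "discontinuation of drug treatment will be mandated only for toxicities attributable to study drug (for Arm A participants", while Arm B toxicities "should be managed according to standard clinical practice, with the goal of maintaining continuous therapy, if possible". At Grade 3, section 7.2 has antiretrovirals "withheld unless the investigator has compelling evidence that the AE has NOT been caused by the study drug", and allows reintroduction after recovery to Grade 2 or lower.

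**The concern.** A between-arm comparison needs an event that can occur in both arms. Two primary components are tied to a drug that only one arm receives. Read literally, the comparator is zero by definition, so the contrast says nothing about how well continued ART is tolerated. Read loosely, the Arm B event must be invented at analysis, by a team that sees adverse events by arm every month (section 9.5).

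The analysis set adds a second problem. A participant who stops for a related adverse event is an event of the discontinuation component and is also someone who has not stayed on regimen. If such participants are removed, the primary analysis loses what it is meant to count.

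**Working it through.** The plan gives no figure for tolerability. Its 24 per arm (section 9.1) was set on FibroScan CAP; that calculation reproduces (20 per arm, 56 dB/m, SD 53: 90.2% power by t-test) but does not bear on this point. The check is therefore mainly a comparison of texts, with illustrations at assumed rates.

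**1. Is an Arm B event defined anywhere?**

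| Section | What it offers for Arm B | What is missing |
|---|---|---|
| 9.3 | A comparison with continued ART | Events are study-drug events only |
| 7.0 | Recognises toxicity due to the entry regimen | No link to the endpoint |
| 8.1 | Lists 14 days off entry regimen under permanent study drug discontinuation | No adverse-event or relatedness condition |
| 9.6.2, 9.6.3 | Related events and stops reported by arm | Still refers to study treatment |

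Sections 7.0, 8.1 and 9.6.1 name study drug and the background or entry regimen separately. An Arm B equivalent may be intended, but none is written.

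**2. What happens to a stopper under 9.6.1?** On the exclusion reading, the participant leaves the set and the event is lost. On the censoring reading, the participant counts up to the stop and the event can be kept. The section supports both.

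**3. Size on the literal reading, stops counted, Arm B fixed at 0/24.** Pearson: N(ad − bc)² / (product of margins).
- 4 v 0: 48 × (4 × 24)² / (4 × 44 × 24 × 24) = 4.36, p = 0.037. Wilcoxon on 0/1 data multiplies this by 47/48, giving 4.27, p = 0.039.
- 3 v 0: 48 × (3 × 24)² / (3 × 45 × 24 × 24) = 3.20, p = 0.074; Wilcoxon 0.077.

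So four stops are needed. At an assumed Arm A related-stop rate of 5%, P(X ≥ 4 of 24) = 1 − (0.292 + 0.369 + 0.223 + 0.086) = 3.0%. At 10% and 15% it is 21.4% and 49.5%, but nothing in the documents supports those rates. Section 2.1 reports no adverse-event discontinuations of bictegravir in Phase II (no denominator, different population).

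**4. Size of the unequal toxicity rules, if entry-ART stops are counted.** Assume a Grade 3 or higher rate of 10% in both arms and a stop probability of 0.7 in Arm A v 0.5 in Arm B. Expected stops are 24 × 0.10 × 0.7 = 1.68 v 24 × 0.10 × 0.5 = 1.20, a gap of 2 points or half a participant. Rejection is 3.2%, against 3.3% with 0.7 in both arms.

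**5. What the replacement can show.** Exact enumeration of two binomials, 24 per arm, for all-cause Grade 3 or higher events: 10% v 10% rejects 4.7%, 20% v 10% 16.7%, 30% v 10% 43.1%. At 20% v 10% the approximate 95% half-width for the difference is 1.96 × √(0.20 × 0.80/24 + 0.10 × 0.90/24) = 20 points. Exact intervals for an Arm A rate: 0/24 gives 0 to 1 − 0.025^(1/24) = 14.2%; 2/24 gives 1.0 to 27.0%.

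**The case against.** The strongest reply is that the wording is merely loose and that study drug here means the assigned regimen. Sections 7.0, 8.1, 9.6.2 and 9.6.3 lean that way. The trial is also a pilot with an exploratory analysis, its objective in section 1.2 is non-comparative, and section 6.4 keeps participants who stop study drug for an adverse event on study. All of this stands and limits the consequence. It does not supply the missing definition or settle the analysis set.

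A reader might infer that the unequal toxicity rules create a false difference against the switch arm. The documents do not support that as a main error. Grade 3 holds are reversible, the Grade 3 component counts events whether or not drug was stopped, and step 4 shows almost no effect on the test. Only an extreme assumption, with every Arm A event ending in a stop and few or none in Arm B, gives large figures.

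A reader might also infer that four stops against none would be a false signal. They would be four real related stops; what is missing is a comparator. That illustration also needs stoppers to be counted, so it cannot be combined with the exclusion reading of section 9.6.1.

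**Conclusion.** The point holds for sections 9.3 and 9.6.1. As written, the between-arm comparison of two primary components has an Arm B count that is zero by wording or undefined. On one of two available readings, the primary set also removes the discontinuation events. The size of any distortion is unknown: every rate above is an assumption, and the little evidence in the documents points to the low end, where a literal test rejects about 3% of the time. The unequal management rules are a caveat for interpretation.

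It would go too far to say that the primary objective cannot be met or that the exclusion is certain. An Arm A rate still answers section 1.2, the HIV-1 RNA component has the same meaning in both arms, and section 9.6.1 can be read as censoring. The change should be made, but the trial does not depend on it.

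**What to change.** Leave the clinical rules as they are and amend sections 9.3, 9.6.1 and 9.6.3.

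1. Base the between-arm tolerability comparison on the proportion with at least one Grade 3 or higher clinical or laboratory event by Week 48, regardless of attribution. Use all randomized participants who started their assigned regimen (Arm B: continued entry ART at baseline), whether or not drug was held or stopped. Give the difference with a 95% CI. Keep study-drug related Grade 3 or higher events as an Arm A rate.
2. In that same population, not the as-treated set, report AE-related discontinuation of the assigned regimen by arm. Give Arm A with an exact 95% CI and list Arm B entry-ART stops beside it without a test. Note that mandated holds and stops apply only to Arm A.
3. Show incomplete follow-up by arm. Under section 6.4 AE stoppers stay on study, so most can be followed to Week 48. That provision is worded for study drug, however, and Arm B participants off entry ART for 14 days leave the study.

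No new data are needed: Grade 2 or higher symptoms, laboratory values and ART changes are already recorded (sections 6.5 and 6.6), and AE summaries by arm exist (section 9.5). The cost is more than wording, because a primary component is redefined and another becomes descriptive. All-cause events are less drug-specific, and power is low.

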### **7.1. Grade 1 or 2 Toxicity**

Participants who develop a Grade 1 or 2 AE or toxicity may continue study drug.

### **7.2 Grade 3 Toxicity**

Participants who develop a Grade 3 AE or toxicity should have all antiretroviral medications, including study drug, withheld unless the investigator has compelling evidence that the AE has NOT been caused by the study drug. The study chair ([name]) should be notified of any Grade 3 or greater toxicity. The subject should be re-evaluated closely until the AE returns to Grade  $\leq 2$ , at which time study drug may be reintroduced at the discretion of [name] or according to standard practice.

If the same Grade 3 AE recurs within 4 weeks following reintroduction and it is thought to be related possibly, probably, or definitely to study drug, then study drug must be permanently discontinued. If the same Grade 3 AE recurs after 4 weeks but is not believed to be related to study drug, the management scheme outlined above may be repeated.

Participants experiencing Grade 3 or greater AEs (requiring permanent discontinuation of study drug) should be followed closely for resolution of the AE to Grade  $\leq 2$ , and [name] must be consulted.

Participants with Grade 3 asymptomatic laboratory abnormalities in cholesterol, triglycerides or bilirubin (if on atazanavir) may continue study drug.

### **7.3 Grade 4 Toxicity**

Participants who develop a Grade 4 symptomatic AE or toxicity will have study drug discontinued. If the site investigator has compelling evidence that the AE has not been caused by the study drug, dosing may resume when the AE has resolved and after consulting [name]. Participants experiencing Grade 4 AEs requiring permanent discontinuation of study drug should be followed closely until resolution of the AE to Grade  $\leq 2$ , and [name] must be consulted.

Participants with Grade 4 asymptomatic laboratory abnormalities in cholesterol or triglycerides may continue study drug.

## **8.0 Criteria For Discontinuation**

### **8.1 Permanent Study Drug Discontinuation**

Study drug discontinuation can occur for the following reasons:

- Drug-related toxicity requiring permanent discontinuation (see Section 7.1).
- Requirement for prohibited concomitant drugs (see section 5.4).
- Request by participant to terminate treatment.
- Confirmation of virologic failure (two measurements of HIV-1 RNA  $>200$  copies/mL at least 2 weeks apart).
- Clinical reasons believed life-threatening by the physician, even if not addressed in the toxicity section of the protocol.
- Participant repeatedly noncompliant with study drug as prescribed.
- Participant discontinues study drug for  $\geq 14$  consecutive days (Arm A).
- Participant discontinues background entry regimen for  $\geq 14$  consecutive days (Arm B).
- Failure by the participant to attend  $\geq 2$  consecutive study visits.

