### *Intervention*

Bictegravir (BIC, GS-9883) is a novel, potent, once-daily, unboosted HIV-1 integrase inhibitor. BIC displays a better *in vitro* resistance profile compared to the integrase strand transfer inhibitors raltegravir and elvitegravir, and is comparable to that of dolutegravir. BIC is being studied in Phase III trials with tenofovir alafenamide + emtricitabine as a once daily regimen for the treatment of HIV infection. In Phase II studies, BIC was well-tolerated, and no discontinuations of BIC for adverse events or clinically significant lab abnormalities occurred. Lipid and glucose levels, and assessments of lean mass, fat mass and bone mineral density with BIC have not yet been released, but would be expected to be similar or improved compared to other integrase inhibitors.

The integrase inhibitor class of agents may be the optimal ART base for TW, although no data exists in this population. However, given interactions between pharmacokinetic boosters and oral hormone therapy, regimens requiring low-dose ritonavir or cobicistat are likely suboptimal for TW on hormone therapy (excluding Stribild/Genvoya and most protease inhibitors). Similarly, due to increased CVD risk in this population, abacavir-containing regimens should likely be avoided (excluding Triumeq). While once daily dosing or single tablet regimens are preferred by most patients, they are especially important for patients with unstable housing and daily life schedules, which are frequent among TW (excluding traditionally-dosed raltegravir). This is also a population with high rates of food insecurity and depression (excluding Complera/Odefsey and Atripla as preferred options). Given these facts, once daily, unboosted bictegravir may be the ideal ART base for TW women. Additionally, female hormone therapy may have adverse effects on bone mineral density, and agents with improved bone health profiles, such as tenofovir alafenamide, will likely be beneficial in this population.

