### **9.6.1 Primary Analysis**

Comparison between treatment arms of the primary endpoint will be undertaken using the Wilcoxon rank-sum test. The primary analysis will be as-treated, excluding participants who do not remain on the study regimen and/or participants who do not have an observed primary endpoint. Participants who discontinue study drug or their background entry regimen for  $\geq 14$  consecutive days will no longer contribute data to the primary outcome after the date on which they first discontinued medication. An intent-to-treat analysis will also be performed as a supplement.

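### Section 8.1's noncompliance stop is worded for Arm A's study drug alone, so the as-treated primary analysis can remove more intermittent nonadherers from the switch arm

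*Combined protocol and SAP*

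**What the plan says.** Section 8.1 opens with "Study drug discontinuation can occur for the following reasons", so the list permits stopping and does not require it. One bullet is "Participant repeatedly noncompliant with study drug as prescribed". It has no arm label and gives no threshold for how many missed doses count as repeated noncompliance.

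The protocol's usage links study drug to Arm A. Section 7.0 says that its management criteria are "mandated only for toxicities attributable to study drug (for Arm A participants" and refers separately to the background or entry regimen for Arm B. The 14-day criterion in Section 8.1 follows the same usage. One bullet, beginning "Participant discontinues study drug for", is labelled Arm A, and a second on the background entry regimen is labelled Arm B. The noncompliance bullet has no such second version.

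Section 9.3 begins the primary endpoint with "The safety (frequency of maintaining HIV-1 RNA <50 copies/mL", compared with continued ART. Section 9.6.1 makes the primary analysis as-treated, "excluding participants who do not remain on the study regimen and/or participants who do not have an observed primary endpoint". It also ends a participant's contribution at the date of first stopping, if she is off study drug or the entry regimen for 14 or more consecutive days. Intent-to-treat is a supplement.

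**The concern.** Adherence bears directly on whether HIV-1 RNA stays below 50 copies/mL. If a rule based on adherence can remove participants from one arm and has no match in the other, the arms being compared are no longer alike in adherence, even though they were randomised.

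Take two participants with the same pattern of scattered missed doses and no gap of 14 days. In Arm A, the investigator may stop study drug for noncompliance. She is then off the regimen, and Section 9.6.1 excludes her or ends her data at the stop date. In Arm B, no listed criterion refers to that pattern. She stays in the analysis set, and any later result of 50 or more counts against continued ART.

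The tilt runs in the direction of hypothesis 1.1.1, that switching maintains virologic control. Three features add to it. The trial is open label, so staff who know the arm decide who is stopped. The threshold is undefined. The protocol itself expects "patients with unstable housing and daily life schedules, which are frequent among TW".

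**Working it through.** **1. The plan's own figure.** The documents give no sample size, margin or expected rate for suppression. The only sizing figure to reproduce is for CAP, a secondary endpoint: difference 56 dB/m, SD 53, two-sided alpha 0.05. A two-sample t-test with 20 per arm has power 90.2%, which agrees with the stated 90%. This says nothing about the suppression comparison, so what follows is an illustration on assumed inputs.

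**2. Routes out of the primary analysis set.**

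| Pattern | Arm A | Arm B |
|---|---|---|
| Off regimen for 14 or more consecutive days | Removed (8.1, 6.4, 9.6.1) | Removed (8.1, 6.4, 9.6.1) |
| Repeated missed doses, no 14-day gap | May be stopped (8.1), then excluded (9.6.1) | No matching criterion; stays in unless withdrawn under 8.2 |
| No observed endpoint | Excluded (9.6.1) | Excluded (9.6.1) |

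The asymmetry is confined to the second row.

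**3. Worst case: every nonadherer leaves Arm A before her RNA counts, and none leaves Arm B.** There is no true difference between arms.

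Assumptions, first set: 3% of adherers and a fraction f of nonadherers are not suppressed, and a share q is nonadherent.

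Arm A as analysed = 0.97. Arm B = 1 − [(1 − q)·0.03 + q·f]. Bias = Arm A − Arm B.

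- q = 0.05: Arm B 95.65% (f = 0.3) or 94.65% (f = 0.5). Bias 1.35 to 2.35 points.
- q = 0.10: Arm B 94.3% or 92.3%. Bias 2.7 to 4.7 points.
- q = 0.20: Arm B 91.6% or 87.6%. Bias 5.4 to 9.4 points.

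For scale, the SE of the difference with 24(1 − q) in Arm A and 24 in Arm B, for q = 0.10 and f = 0.5, is √(0.97·0.03/21.6 + 0.923·0.077/24) = 6.6 points, so the bias is 0.72 SE. For q = 0.20 and f = 0.5 it is 9.4/7.8 = 1.2 SE.

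Assumptions, second set: 24 per arm, suppression 95% in adherers and p = 50% or 70% in nonadherers, with k = 1 to 5 nonadherers per arm (1/24 = 4% to 5/24 = 21%).

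Bias = 0.95 − [(24 − k)·0.95 + k·p]/24 = k(0.95 − p)/24.

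- p = 0.70: 1.0 point (k = 1) to 5.2 points (k = 5).
- p = 0.50: 1.9 points (k = 1) to 9.4 points (k = 5).

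**4. Allowing for Arm B's 14-day rule.** Suppose it removes half of Arm B's nonadherers.

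Second set: Arm B = [(24 − k)·0.95 + (k/2)·p]/(24 − k/2). For k = 5 and p = 0.50, this is (18.05 + 1.25)/21.5 = 89.8%, a bias of 5.2 points. Over the grid the bias is 0.5 to 2.9 points (p = 0.70) or 1.0 to 5.2 points (p = 0.50).

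First set, with the same change: 1.4 to 2.5 points at q = 0.10 and 3.0 to 5.2 points at q = 0.20.

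**5. Same rule in both arms, or all randomised participants analysed.** The bias in this illustration is 0.

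**The case against.** A reader might infer that poor adherers are removed from the switch arm only. The documents do not support that. Sections 8.1 and 6.4 also discontinue Arm B participants who stop their entry regimen for 14 or more consecutive days, and Section 9.6.1 applies its 14-day cut-off to both arms. Section 8.2 lets the investigator end study participation in either arm. What remains one-sided is the criterion for intermittent nonadherence.

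A reader might also infer that the missed-visits bullet ("Failure by the participant to attend" two or more consecutive visits) acts on Arm A alone because the list concerns study drug. That does not hold. The bullet has no arm label, the same list contains an Arm B bullet, and lacking an observed endpoint excludes participants from either arm.

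Nor does the plan require noncompliant participants to be taken off drug. It says that this can occur, and nothing shows how often the criterion would be used.

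The step 3 figures are a worst case. RNA is scheduled at weeks 4, 12, 24 and 48, so a result may already have counted before a stop. The 20% in Section 9.1 is total discontinuation or loss, not intermittent nonadherence, and does not support q = 0.20.

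There are safeguards. Intent-to-treat is planned, Section 9.6.3 reports discontinuations by arm and lists the reasons for stopping study drug, and the trial is a pilot with exploratory analysis. These make differential removal visible. They do not repair the primary result, because intent-to-treat is a supplement and its handling of missing RNA is not stated.

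**Conclusion.** The point holds in a limited form. Section 8.1 contains an extra, undefined and discretionary noncompliance criterion worded for study drug, with no counterpart for the entry regimen. Combined with the as-treated rule in Section 9.6.1, it can remove more intermittent nonadherers from Arm A than from Arm B, which favours the switch on the first component of the primary endpoint.

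The size cannot be derived from the documents. It rests on these assumptions: no true difference, 3 to 5% non-suppression in adherers, 30 to 50% in nonadherers, and about 4 to 21% nonadherent. On those inputs the bias is about 1 to 9 points as a worst case with wholly one-sided removal, and about 0.5 to 5 points if Arm B's 14-day rule removes half of its nonadherers. With 24 per arm, one participant is 1/24, or about 4 points. The bias is modest against sampling error, but it has a predictable direction and is cheap to avoid.

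**What to change.** In Section 9.6.1, state that a stop for noncompliance does not remove a participant from the primary virologic comparison. She is analysed in her randomised arm with all observed HIV-1 RNA counted, including the result at the Early Discontinuation visit. The sentence must say that it overrides the 14-day cut-off. Otherwise a participant permanently stopped for noncompliance reaches 14 days off drug, and her data end at the stop date anyway.

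Add one rule for missing HIV-1 RNA and apply it to both arms. This is needed because Section 6.2 provides a discontinuation visit only after 12 or more weeks of study drug, so an earlier stop may yield no result.

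Alternatively, if an adherence-based exclusion is kept, define it objectively and identically in both arms, in terms of the assigned regimen.

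The bullets in Section 8.1 must be reconciled so that the arm to which each applies is explicit. The clinical stopping rule itself is for the study team.

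The cost is a few sentences in Section 9.6.1 and arm labels in Section 8.1. The Early Discontinuation HIV-1 RNA is already scheduled, although it will not exist for every early stop. The downside is that Arm A's suppression figure may be slightly less favourable.
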